Based on preliminary data, we expect to observe larger age differences in DA D2-like receptor availability in the pallidum and frontal cortical regions, but smaller (but measurable) declines in the ventral striatum. We hypothesize that middle-aged adults will show significantly lower levels of DA release in the striatum and medial prefrontal cortex and DAT expression in the striatum compared to younger adults. Across both groups, we expect individuals with greater DA release in the ventral striatum and ventromedial prefrontal cortex to be more tolerant of effort costs.

Aim 2: To examine the influence of individual and age-related differences in DAT on dAMPH-induced DA release. Given that DAT is the primary site on which dAMPH acts, we will test the hypothesis that individual differences in DAT expression substantially predict DA release and the subjective effects of dAMPH. Because DAT declines with age, we additionally hypothesize that dAMPH-induced DA release will be lower in the middle aged than the young adult sample. We additionally predict that the combination of DA midbrain autoreceptor levels and striatal DAT levels will predict dAMPH induced DA release better than either index in isolation.

Aim 3: To examine the influence of dAMPH-induced DA release on cost-benefit decision making in young adulthood and late middle age.

We recently demonstrated that dAMPH increases tolerance of physical effort costs in healthy young adults. Young and middle-aged adults will complete a behavioral version of the effort-based task in two sessions (placebo, dAMPH). We expect that tolerance of physical effort will be increased under dAMPH in both age groups, with differences in the extent of modulation correlating with measures of baseline DA functioning and DA release.

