4.0 Study Procedures

4.1 Primary Study Procedures: The study involves 4 sessions: Informed Consent, Fallypride PET + placebo, Fallypride PET + oral d-amphetamine, and PE2I PET. The 3 PET sessions will be conducted within a 6 week window, and whenever possible within a 2 week time period.

4.2. Informed consent session: Informed consent will be obtained by [name] or approved study personnel after inclusion and exclusion criteria have been reviewed. This will be done in the Dept. of Psychology at Vanderbilt University. Written consent materials are provided to the participant originally when they complete the related IRB protocol #141812. Although given to participants during Part I of the study, Participants only sign the consent for the 2nd part of the study after completing the prior study and passing inclusion and exclusion criteria assessed during that study.

In the present study, participants are given time to read (or reread) the written informed consent document in a quiet private room. They are asked if they have any questions about the protocol. If they have no questions or the researcher has any concerns about whether they understand the procedures, the researcher will briefly review the steps of the study. Because the participants will have already completed IRB #141812, the researchers will already have some knowledge of the participants level of cognitive functioning, and if there is a concern about the participants ability to understand the procedures based on their past performance on cognitive measures they will be excluded from the study.

After the potential participant indicates they have read the document, [name] or his associate will briefly review specific procedures and their risks (especially those related to administration of amphetamine and PET radioisotopes), and the subject will be given a chance to ask questions. The participants will only be asked to sign the informed consent document after any and all questions have been answered.

After signing the informed consent, participants will receive a brief training on how to perform the two-stage task (this will help reduce the amount of time needed for training on that task on the fallypride PET scan days). Participants will also complete the Tests of Vigilance and Attention (TOVA: <http://www.tovatest.com/>), which assesses attention abilities and motor impulsivity.

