4.3 Specific procedures for female subjects of child-bearing potential: Premenopausal without hysterectomy or similar procedure, will need to have an additional blood draw within 48 hours prior to each PET session to rule out pregnancy (blood drawers will typically be scheduled within 36 hours preceding the planned time of radioisotope administration). Women who are premenopausal will be only studied within the first 10 days of their menstrual cycle.

4.4 Fallypride PET Sessions (with placebo or oral d-amphetamine).

Participants complete two [¹⁸F]fallypride PET sessions, each lasting approximately 7 hours. Scan sessions will all start in the afternoon. Subjects will be instructed to have a moderate lunch with no more than a single cup of coffee or tea before coming to the PET center. If the scan is not expected to start until after 5 PM, a light snack may also be eaten. After determination of blood pressure, respirations, pulse, temperature, an intravenous line will be placed in the forearm, the subject will complete ratings of their mood (using the and PANAS and the Amphetamine Interview Schedule administered on a laptop computer), and participants will have a brief neurological exam conducted by one of the study MDs. An initial blood sample for genotyping or estradiol levels (women only) will be acquired.

The subject will then receive a 0.43 mg/kg oral dose of d-amphetamine or placebo. The investigational pharmacy will prepare capsules with 10 mg, and 2.5 mg with dosing rounded to the nearest 2.5 mgs (for instance an individual weighing 80 kg would be rounded up to a 35 mg dose). The drug dose and placebo, will be placed by the pharmacist in identical containers, labeled with the subject's ID and scan day number. A sealed envelope indicating whether the dose is d-amphetamine or placebo will be included in case there is a need to break the blinding. The study physician, can quickly access this information if there is appearance of an adverse drug effect. Otherwise the study physician and experimenters who have contact with the participant will remain blind until the participant has completed their second PET scan. If a participant has an adverse event that necessitates any medication, or other intervention, the blind will be broken to the participant.

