Aim 2 examines the hypothesis that individual and age-related differences in DAT are associated with dAMPH-induced DA release. This will be studied using striatal ROIs and ANOVA with age group serving as a between subjects variable.

Aim 3: To examine the influence of dAMPH-induced DA release on cost-benefit decision making in young adulthood and late middle age. We expect that tolerance of physical effort will be increased under dAMPH in both age groups, with differences in the extent of modulation correlating with measures of baseline DAT functioning and DA release. This will be accomplished by ANOVA analysis with age group as a between subjects variable.

Mediation Analyses: In each of the above cases we will utilize a mediation analysis to test whether expected age differences in behavior (effort performance, responsivity to d-AMPH) are mediated by age related differences in regional DA functions.

Exploratory voxel-wise analyses: Beyond the ROI analyses, more exploratory whole-brain voxelwise analyses will be conducted. For these analyses, individual difference measures (e.g., choice preferences, trait affect, cognitive ability, etc) and age will be mean-deviated and entered as regressors of interest to predict BP_{ND}. The resulting whole-brain maps will be thresholded at whole brain $p_{\text{cluster-corrected}} < 0.05$.

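### The plan sets no balanced order for the placebo and d-amphetamine sessions within age group and sex, and the Aim 3 model has no session-order term

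*Combined protocol and SAP*

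**What the plan says.** Aim 3 (Section 2.0) is a within-person comparison: "Young and middle-aged adults will complete a behavioral version of the effort-based task in two sessions (placebo, dAMPH"). The change in BP_ND that Section 7.0 uses for dopamine release comes from the same pair of sessions.

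Section 4.1 lists the visits as "Informed Consent, Fallypride PET + placebo, Fallypride PET + oral d-amphetamine, and PE2I PET", without saying whether this is the running order. Under Section 4.4 the containers are identical and "labeled with the subject's ID and scan day number". It adds: "A sealed envelope indicating whether the dose is d-amphetamine or placebo will be included". The study physician and the experimenters in contact with the participant "will remain blind until the participant has completed their second PET scan". Section 4.44 has blood drawn on the placebo day too, with a sealed form telling the laboratory whether to assay or discard it.

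No section says who sets the order, by what method, in what ratio, or whether it is balanced within age group or sex. The varying order in Section 4.41 is that of tasks within a session.

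For the Aim 3 analysis, Section 7.0 says: "This will be accomplished by ANOVA analysis with age group as a between subjects variable". Drug is not named as a within-subject factor, and there is no session or order term.

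**The concern.** The EEfRT, the two-stage task, the cognitive tests and the fallypride scan are each done twice, preferably within two weeks. Practice, fatigue or habituation can shift second-session results in either direction. In a two-session crossover that shift is handled by balancing the order and by fitting a term for it. The plan documents neither.

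Two things are at stake. If order is balanced but not modelled, the session effect stays in the residual variance of the drug contrast and costs power. If order is left to chance, the age groups can end up with different shares of drug-first participants, and part of the session effect then appears as an age-by-drug interaction. That comparison matters because the Aim 3 drug effect is to be examined by age group.

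**Working it through.** **The plan's own figure.** Section 7.0 gives 60 participants (30 per group) for an age-group difference of d = 0.75, power 0.80, two-sided 0.05. The normal approximation is 2 × (1.960 + 0.842)² / 0.75² = 27.9, so 28 per group. The exact noncentral t gives 29 per group, and power at 30 per group is 0.815. The figure reproduces, but it concerns the age contrast. The plan states no power for drug versus placebo.

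**Inputs.**
- From the documents: 60 completers, 30 per age group, equal gender (Section 3.2); two-sided 0.05 (Section 7.0).
- Assumed, because the documents give neither: a drug effect of 0.37, which yields about 80% power, and session effects δ of 0.3, 0.5 and 0.8.
- Unit: the SD of the within-person drug-minus-placebo difference, given order.

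**Model.** Dᵢ = drug effect + δsᵢ + eᵢ, with SD(e) = 1, sᵢ = +1 if drug came second and −1 if it came first.

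**Balanced order (30:30), power for the drug contrast.** With an order term the noncentrality is 0.37 × √60 = 2.87 and power is 0.80 for any δ. Without the term, δ cancels from the mean but stays in the estimated variance, which rises to about 1 + δ². Treating the effect as 0.37/√(1 + δ²) slightly overstates the loss, so simulation is the better guide.

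| δ | 0.37/√(1 + δ²) | Approximate power | Simulated power | With order term |
|---|---|---|---|---|
| 0.3 | 0.354 | 0.77 | 0.78 | 0.80 |
| 0.5 | 0.331 | 0.71 | 0.73–0.74 | 0.80 |
| 0.8 | 0.289 | 0.60 | 0.62 | 0.80 |

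With no drug effect, the simulated false-positive rate without the term falls below 5% (4.2% at δ = 0.3, 2.8% at δ = 0.5). The harm here is lost power, not bias.

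**Simple randomisation, age-by-drug interaction.** If drug-first counts are two independent Binomial(30, 0.5) variables, P(difference ≥ 6) = 0.155, about 16%. A difference of k participants shifts the interaction by 2δk/30. At k = 6 this is 0.4δ, or 0.12, 0.20 and 0.32 SD. Simulated false-positive rates with no true effect and no order term are:

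| δ | All allocations | Difference of 6 or more |
|---|---|---|
| 0.3 | about 5% | about 8% |
| 0.5 | about 5% | about 11% |
| 0.8 | about 5% | about 17% |

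**Fixed order, for reference only.** If everyone took placebo first, sᵢ = +1 throughout and the drug estimate is drug effect + δ. With no drug effect, shifts of 0.2, 0.3 and 0.5 SD give false positives in 33%, 63% and 97% of trials. Drug and session are then completely aliased, so an order term cannot be estimated.

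**The case against.** The strongest reply is that order clearly varies. Identical containers labelled by scan day, a sealed code, staff kept blind to the second scan, and a sealed assay-or-discard form would serve little purpose if day 1 were always placebo. That stands. A reader might infer from the list in Section 4.1 that placebo always came first and that practice could pass for a drug effect at the 33%, 63% or 97% rates. The documents do not support this: the list names session types, and the blinding procedures make a fixed order unlikely.

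A second reply is that chance imbalance under randomisation is random error, already reflected in the standard error. That also stands unconditionally, and the 16% figure must not be read as a 16% risk of a false result. Once a large imbalance has occurred, though, the rates above apply, and stratified blocking with an order term would avoid them cheaply.

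Third, participants meet the EEfRT in Part I and train on the two-stage task at consent, and the EEfRT outcome is a choice rather than a skill score. This probably reduces practice gain but does not exclude it, or fatigue or habituation. Nor do the documents give a mechanism by which task practice would alter change in BP_ND, so the order covariate there is a precaution.

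None of these replies supplies an allocation scheme or a model term.

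**Conclusion.** The concern holds as a gap in specification. Varied order is implied, balanced order is not stated, and the Aim 3 model omits session order and does not name drug as a within-subject factor.

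The cost under balanced order is small at δ = 0.3 and material at δ = 0.8. Under simple randomisation the overall error rate is sound, and the age-by-drug result is distorted only when a marked imbalance happens to arise. All sizes rest on the assumed 0.37 SD drug effect and the assumed session effects; the documents give no estimate of either.

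It does not follow that the order was fixed or that the drug effect is confounded. A figure in Section 4.4 was not available in the text read. If it sets the order, the allocation half of the point falls away, but the missing model term does not.

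**What to change.** 1. In Section 4.4, state that the investigational pharmacy assigns drug-first or placebo-first from a blocked list stratified by age group and sex. Equal gender within 30 per age group means 15 per stratum. Blocks of even size with equal numbers of each order (2 or 4, say) would put 7 or 8 of the 15 drug-first. Each age group then has 14 to 16, and the groups differ by at most 2 among those completing. Because staff may learn the code after the second scan, the pharmacy should vary the block size and hold the list.
2. In Section 7.0, specify Aim 3 as drug (within-subject) by age group, with session order as a between-subject factor. Include its interaction with drug, since that interaction carries the session effect. Equivalently, regress each participant's drug-minus-placebo difference on age group and effect-coded order.
3. Add order as a covariate wherever change in BP_ND or the drug effect is the outcome.
4. If participants are already enrolled, report the realised order by age group and add the term. If the order proves to have been fixed, adding the term cannot work: drug and session cannot be separated, and the Aim 3 drug-effect conclusion must say so.

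Cost: one pharmacy list, short additions to Sections 4.4 and 7.0, and one degree of freedom in the analysis of the differences.

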Subjects will have blood pressure and pulse determinations every 30 minutes for the first 2.5 hours, prior to the start of PET scanning (around 175 minutes post-administration) and every 60-70 minutes thereafter until the subject's blood is in the normotensive range. In the event that the participant's blood pressure exceeds 180 mm Hg systolic, blood pressure will be measured every 15 minutes until it shows evidence of reducing (at least a 5 mm Hg decline). In the unlikely event that a subject's blood pressure should rise to greater than 200 mm Hg systolic B.P. for over 30 minutes, the patient may be treated with oral clonidine at the discretion of the study MD (see risk section below for specific details). We note that in our multi-year experience working with oral amphetamine, we have never required an intervention.

After .5, 1, 1.25, 1.5, 2, 3, hours post-dAMPH/placebo administration and after the first two PET scans, approximately 4 and 5 hours subjects will complete ratings of mood (with selected items from the Amphetamine Interview Schedule and PANAS) and the DEQ (which asks them to rate whether they feel the drug, feel high, like the drug, or want more of the drug). Subjects will make their ratings on a laptop computer.

[figure not shown]
4.41 Cognitive Assessments. To further assess the cognitive specificity of dAMPH effects on cognition, participants will complete a battery of cognitive measures under placebo and drug. After the 60-minute post-administration blood pressure, mood ratings and blood draw, participants will begin performing the cognitive assessments tasks. Testing will include measures of speed of processing [WAIS-III Digit Symbol Coding and Symbol Search [115]], a measure of the speed of verbal associations [Controlled Oral Word Association Test [116]], and a measure of motor speed [finger tapping [151]] and a measure of working memory (2-back task). All tasks are included based on literature indicating that these functions are modulated by DA (e.g., [124,125]), with the tasks starting immediately following the amphetamine. The precise order of these tasks will vary, with brief tasks occurring during the 60-75 post-administration period, and the other tasks occurring following the 90 minute blood pressure and mood ratings.

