4.44 Post administration blood draws. 4 blood draws (3 ml each) are taken to measure plasma amphetamine levels. These are collected at 30, 60, 90, and 175 minutes post-amphetamine. In order to avoid a different blood draw schedule, blood draws will additionally be made on the placebo day and will be discarded using appropriate hazardous biospecimen procedures. The lab will receive a sealed form that indicates whether to analyze or discard the samples.

4.45 PET scanning and fallypride administration. Scanning will be accomplished with a GE Discovery STE PET/CT scanner. 5 mCi of [¹⁸F]fallypride (specific activity > 3,000 Ci/mmol) will

be injected, and subjects will be scanned for 3.5 hours (with two 15 minute breaks) to allow estimates of both striatal and extrastriatal binding potential. Dots are placed on the subject's forehead and cheeks for periodic visual checks of alignment throughout the scan period, and for repositioning after breaks. Three CT scans will also be collected during each session for attenuation correction. Blood pressure will be taken during each break and mood ratings will be taken during each break. During the second break participants will be given a high fat meal to help improve elimination of the radioisotope. Participants will also be given fluids to drink and asked to void their bladder.

At the conclusion of each PET scan on drug and placebo day, vital signs-blood pressure, pulse, temperature and respirations – will be measured, a brief motor neurological examination performed, and an additional 3.5 ml of blood drawn for a CBC and a comprehensive metabolic panel (CMP). If neurological exam and vital signs are normal the participants will be released from the study. In the unlikely event that they are not normal, the participant will be asked to stay under medical supervision in the VUMC (in one of the rooms in the PET center) until these measures have normalized. At the time of release participants will be given instructions to drink fluids and void their bladder at least once every two hours for up to 6 hours after the time of the start of the PET session.

4.5 *FE-PE2I PET Session*

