Administration of Amphetamine: The primary risks associated with the use of dAMPH include an increase in blood pressure, psychological effects (i.e. feeling jittery, anxiety, increased alertness and restlessness), and difficulty sleeping. Numerous studies of oral dAMPH in normal volunteers have been reported. A 0.5 mg/kg oral dose of dAMPH produced a mean elevation of 28 mm Hg increase in systolic blood pressure at 2 hours, i.e. a peak systolic blood pressure of 148 which decreased to a 14 mm Hg increase at 4 hours and returned to normal levels by 6 hours. The pulse rate remained unchanged [145,176]. Our own data in young adults exposed to our standard dose of 0.43 mg/kg indicates a mean increase of approximately 27 mm HG at peak (148 mm Hg) that occurs by 3 hours, and decreases substantially by completion of scanning. Based on these data we anticipate that a 0.43 mg/kg dose of dAMPH should produce blood pressure elevations of 25-30 mm Hg on average. To limit risk, we apply strict blood pressure restrictions on enrollment (systolic no more than 150 mm Hg). The average systolic blood pressure is 120 (average range: 108-133) for the age range 20-30, and 130 (average range: 116-144) for the age range 50-60. With an inclusion cutoff of 150 mm Hg, we do not anticipate many participants exceeding 180 mm Hg on dAMPH. This is within the normal range for systolic blood pressure for exercise (160 - 220 mm Hg). Participants with a reported history of labile hypertension will also be excluded, since they would be at increased risk for a blood pressure elevation. Participants will also be given an EKG and will be excluded if there are any abnormalities that would represent a risk under a condition of temporary elevation of blood pressure. Participants' blood pressure will be monitored by medical staff during their time in the study (every half hour), and standard of care intervention will be administered if there is a sustained elevation in blood pressure > 200 mm Hg

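### The 15-minute blood-pressure checks can end after a 5 mm Hg fall at any level, so during scanning the rule for pressure above 200 may have no required reading when it is reached

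*Combined protocol and SAP*

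**What the plan says.** Section 4.4 (Fallypride PET Sessions) schedules readings every 30 minutes for the first 2.5 hours after dosing, then before scanning at about 175 minutes, "and every 60-70 minutes thereafter until the subject's blood is in the normotensive range". Above 180 mm Hg systolic a closer schedule applies: "blood pressure will be measured every 15 minutes until it shows evidence of reducing (at least a 5 mm Hg decline". No target level is named, and the reading from which the fall is measured is not defined. The next sentence lets the study physician give clonidine should pressure "rise to greater than 200 mm Hg systolic B.P. for over 30 minutes", and refers to the risk section for details.

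The scan timetable fits the longer interval. Section 4.4 says that "after the first two PET scans, approximately 4 and 5 hours subjects will complete ratings of mood", and Section 4.45 adds: "Blood pressure will be taken during each break and mood ratings will be taken during each break".

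Section 5.0 (Administration of Amphetamine) says something different: participants' "blood pressure will be monitored by medical staff during their time in the study (every half hour". The same sentence commits to intervention for pressure above 200 sustained for more than 30 minutes. Section 5.0 also requires that the study physician, who is in the PET suite or on the medical campus, be told at once of any reading above 170. On frequency it states: "we do not anticipate many participants exceeding 180 mm Hg on dAMPH". It reports a mean rise of about 27 mm Hg "at peak (148 mm Hg) that occurs by 3 hours, and decreases substantially by completion of scanning".

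**The concern.** Two adjacent sentences of Section 4.4 work against each other. The treatment rule asks whether pressure has stayed above 200 for more than 30 minutes, which needs a reading at about that time. The stop rule can switch those readings off after one small fall, because it looks at the direction of change and not at the level reached. A participant at 212 and then 206 satisfies the stop rule while still above the treatment threshold.

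Before scanning, the 30-minute routine readings largely cover this. From scan start the routine interval lengthens to 60-70 minutes, close to the time of the mean peak. A participant could then lie in the scanner with a last recorded pressure above 200 and no further reading required for some time. Many such falls will be real, since pressure drops substantially by the end of scanning, but the rule cannot tell a real recovery from a brief dip. What is at stake is participant safety; no efficacy analysis is affected.

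**Working it through.** **1. The routine interval.** Section 4.45 gives 3.5 hours (210 minutes) of scanning with two 15-minute breaks. Assuming three equal blocks, each lasts (210 − 30)/3 = 60 minutes if the breaks fall inside the 3.5 hours, or 210/3 = 70 minutes if outside. This reproduces Section 4.4's 60-70 minutes and agrees with Section 5.0, which says participants lie still for up to 70 minutes. Readings at about 175, 240 and 300 minutes give intervals of 240 − 175 = 65 and 300 − 240 = 60.

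**2. Routine trigger, routine clock kept.** Let the first reading above 200 be a routine one at time t, with a fall of at least 5 seen at +15 and pressure still above 200. A later routine reading above 180 is taken to restart the checks. Required readings after t:

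| t (minutes after dose) | Section 4.4 as written |
|---|---|
| 30 to 120 | +15, +30, +45 |
| 150, with a separate reading near 175 | +15, +25, +40 |
| 150, without one | +15, then +60 to +70 |
| about 175 or later | +15, then +60 to +70 |

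In the last two rows the time without a required reading after the recheck is 60 − 15 = 45 to 70 − 15 = 55 minutes. With half-hourly routine readings, as in Section 5.0, the sequence is +15, +30, +45 and there is no gap.

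**3. Off-schedule trigger near scan start.** A participant between 180 and 200 may already be on 15-minute checks, so the first reading above 200 can itself be a recheck. The next routine reading after 175 falls at 175 + 60 = 235 to 175 + 70 = 245 minutes.

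- First above 200 at 190, fall seen at 205: 235 − 190 = +45 to 245 − 190 = +55.
- First above 200 at 180, fall seen at 195: +55 to +65.
- First above 200 at 165, fall seen by 175-180: +70 to +80.

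These examples span +45 to +80. A recheck later in a scan block lies nearer the next routine reading, and the gap shrinks accordingly.

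**4. Routine clock reset at the recheck.** 15 + 60 = +75 to 15 + 70 = +85.

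**5. How extreme the event is.** In whole mm Hg, ending the checks above 200 needs a recheck of at least 201, so a first reading of at least 201 + 5 = 206.

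- From the 150 entry limit: 206 − 150 = 56, and 56/27 = 2.1 times the mean rise.
- From the 145 limit for those over 60: 206 − 145 = 61, and 61/27 = 2.3 times.
- From Section 5.0's average of 130 (ages 50-60): 206 − 130 = 76, and 76/27 = 2.8 times. From 120 (ages 20-30): 206 − 120 = 86, and 86/27 = 3.2 times.

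Ending the checks while still above the 180 trigger needs only 181 + 5 = 186. From the 150 limit that is a rise of 36, and 36/27 = 1.3 times the mean. The documents give no spread for individual readings, so these ratios cannot be turned into a frequency.

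**6. With a stopping level.** On the path 212 at time 0 and 206 from +15 (values assumed), requiring pressure at or below 180 before stopping gives readings at +15, +30, +45 and +60.

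**The case against.** **The risk section may govern.** Section 4.4's treatment sentence points to Section 5.0, where half-hourly monitoring and the above-200 rule stand in one sentence. At that interval there is no gap. This is the strongest objection, and it makes the gap conditional on Section 4.4. It does not settle the matter: the pointer may concern only drug details, and readings at scan breaks in Section 4.45 match 60-70 minutes. The two intervals conflict whichever governs.

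**The wording is open to a safer reading.** The recheck of 206 is itself above 180 and could be taken to restart the checks. The 5 mm Hg figure could also be a minimum for judging that pressure is coming down, without being sufficient alone. Both readings are possible. The literal sense of the stop rule still allows the checks to end, and a safety instruction should not depend on which sense staff choose.

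**A physician is already involved.** Anyone above 200 has passed the 170 alert, a physician is nearby, Section 5.1 describes real-time monitoring of vital signs, and treatment is discretionary in Section 4.4. This lowers the risk considerably, though none of it sets when the next reading is due. A reader might infer that participants are left unsupervised; the documents do not support that.

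**The event is remote.** Labile hypertension and risky EKG findings are excluded, and the investigators report never having needed to intervene after amphetamine. This largely stands, with Section 5.0's own caveat that most past subjects were under 40, whereas half of this sample is planned from the older group.

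**The timing is not a single number.** A reader might infer that treatment is always assessed 15 to 40 minutes late. That range compares +60 to +70 with a reading at +30 (30 to 40 minutes) or, taking more than 30 minutes strictly, at +45 (15 to 25 minutes). It holds only for a routine trigger with the clock kept under Section 4.4, and steps 3 and 4 show how the interval moves otherwise.

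**Conclusion.** The point holds as a low-probability safety wording fault. Read literally, Section 4.4 lets the 15-minute checks end with systolic pressure above 180 or above 200. Once scanning has started, the next required reading can then come well after the 30-minute mark that the treatment rule depends on: +60 to +70 minutes for a routine trigger with the clock kept, and differently under the other assumptions worked above.

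This rests on three assumptions: that Section 4.4 governs over Section 5.0's half-hourly interval, that the fall ends the checks whatever the level, and that the physician orders no extra reading. The documents do not support a claim about the whole session, since the earlier 30-minute schedule and a pre-scan reading near 175 minutes cover the period before scanning. Nor do they support any claim about how often this would happen.

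**What to change.** In Section 4.4, continue the 15-minute checks, including during scanning, until systolic pressure is at or below 180 mm Hg (or a lower level set by the study physicians) and falling. Restart them at any later reading above 180. State one routine monitoring interval in both Section 4.4 and Section 5.0, with the break readings in Section 4.45 made consistent with it.

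This takes a few sentences of protocol wording. In rare participants it means some extra cuff readings and possibly an interrupted scan, with some loss of PET data for that session.
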